### **Cognition:**

- Cognitive assessment battery:

Intellectual Functioning Estimate

1) Wechsler Test of Adult Reading (WTAR) - Word reading tests are an established method of establishing a premorbid estimate of verbal intellectual functioning, which will serve as an estimate of premorbid cognitive reserve.

Visuospatial construction

2) Rey-Osterrieth Complex Figure (ROCF) Test- is a widely used neuropsychological test for the evaluation of visuospatial constructional ability (Copy trial) and visual memory (Immediate Recall, Delayed Recall, and Recognition trials). It consists of three test conditions: Copy, Immediate Recall and Delayed Recall.

#### Attention/Processing Speed/Executive Functioning

3) Trail making tests – is a neuropsychological test of visual attention and task switching. It consists of two parts in which the subject is instructed to connect a set of 25 dots as fast as possible while still maintaining accuracy. It can provide information about visual search speed, scanning, speed of processing, mental flexibility, as well as executive functioning.

4) Symbol Digit Modalities Test (SDMT) - The SDMT is a measure of processing speed and working memory that has proven to be sensitive to cognitive impairment in MS that has both oral and written trials (only the oral trial will be administered given the anticipated difficulty patients will have with tremor). Subjects are presented with a key at the top of a page pairing unique symbols with single digits. Subjects are required to provide the correct digit with symbols that are presented on the rest of the page. The number of correct responses provided in 90 seconds on the oral and written trials, respectively, is recorded.

5) Paced Auditory Serial Addition Test (PASAT) - The PASAT is a more complex measure of processing speed and working memory in which a series of digits is presented to subjects at varying intervals (i.e., 2 seconds, 3 seconds). Subjects must add each digit to the immediately preceding digit for the duration of each trial. The number of correct responses for each trial is recorded.

6) Controlled Oral Word Association Test (COWAT) - The COWAT is a measure of speeded verbal fluency and word retrieval in which subjects are asked to say as many words as they can that begin with each of three letters for 60 seconds. The total number of words generated across all three trials is recorded.

#### Memory Functioning

7) Hopkins Verbal Learning Test-Revised (HVLT-R) - The HVLT-R is a measure of verbal learning and memory in which subjects are asked to learn a 12-item word list over three trials (total immediate learning). A delayed free recall trial is administered after 20 minutes, followed by a yes/no recognition trial.

#### Language functioning

8) Semantic Verbal Fluency – Semantic Verbal fluency is a measure of speeded verbal fluency and word retrieval in which subjects are asked to say as many animal names/fruits and vegetables for 60 seconds. The total number of words generated across all three trials is recorded

#### Motor testing

- Rapid Paced Walk (RPW) test: The RPW assesses stride length, balance and overall mobility, all of which can be impaired in PD [Crizzle AM, et al. 2013].

#### Quality of Life

- Parkinson's Disease Questionnaire (PDQ-39): is a reliable, valid, responsive, acceptable and feasible as the tool for the assessment of quality of life in Parkinson's disease patients. There are

39 questions in the long form Parkinson’s Disease Questionnaire, with 8 discrete scales: mobility (10 items), activities of daily living (6 items), emotional well-being (6 items), stigma (4 items), social support (3 items), cognitions (4 items), communication (3 items), and bodily discomfort (3 items). Patients are asked to think about their health and general well-being and to consider how often in the last month they have experienced certain events. Patients are asked to indicate the frequency of each event by selecting one of 5 options (likert Scale): never/occasionally/sometimes/often/always or cannot do at all.

- EuroQoL-5 Dimension-5 level (EQ-5D-5L): consists of 2 pages-the EEQ-5D-5L descriptive system and the EQ Visual Analogue Scale (EQ VAS). The descriptive system comprises 5 dimensions: mobility, self care, usual activities, pain/discomfort, anxiety/depression. Each dimension has 5 levels: no problem, slight problems, moderate problems, severe problems, and extreme problems. This is a widely used well validated simple assessment that is comparable across disease populations.

4. By assessing and comparing the proportion of subjects that drop out of the study due to study drug intolerance in the two groups (treatment vs. placebo).

**Secondary Specific Aim:** To examine the effect of CBD on severity & duration of tremor in PD.

**Secondary Outcome Measure:** Tremor is measured by the change from baseline to 10th day of 5 mg/kg/day (week 2 and week 12) and the end of each treatment phase (week 7 and week 17) change in total of scores on items 3.17 and 3.18 in part III of the MDS-UPDRS in the ON state (when anti-PD medication is working). Item 3.17 is rest tremor amplitude. Extremity ratings range from 0: Normal, No tremor to 4: Severe, >10 cm in maximal amplitude. Lip/Jaw ratings are similar but smaller amplitudes. Item 3.18 is constancy of rest tremor: 0 (no tremor) to 4 (present >75% of the exam).

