**Principal Investigator: [name] [name]**

**Version Date: 12May2017**

## **I. Hypotheses and Specific Aims:**

Parkinson disease (PD) is a relatively common, progressive, disabling disorder that responds partially to symptomatic treatments. Since cannabis has become legal in Colorado, many persons with PD have been trying it to see if it relieves any of their symptoms. According to published and anecdotal reports cannabidiol (CBD), is a component of cannabis, has potential beneficial medical uses. However, the safety, tolerability, dose and benefits are unknown.

There are many forms of CBD being marketed. In this study we are using Epidiolex, because it is >99% pure CBD with only a trace amount of THC (<0.15%) and because it has more data on it regarding safety, tolerability, dosing and efficacy than most other forms. It is manufactured by GW Pharmaceuticals and currently it is being used in four FDA approved epilepsy studies. GW has determined a dose range that is best tolerated and effective in psychosis and seizure disorders. These studies are described in the Investigational Brochure (IB) Edition 8, Section 7.3.1. The largest cohort of subjects have been in epilepsy studies, and the majority of them were pediatric. Because there is no definitive published data on what dose of Epidiolex is best tolerated and effective in an adult population with a neurodegenerative disease, PD, this study is conducted in two stages.

- The major purpose of the Stage 1 is to study the safety and tolerability of the proposed dosage regimen, which is based on GW Pharmaceutical's experience. This is an open label study in 10 subjects, during which the dose is gradually increased to the manufacturers recommended target dose, with tolerability being evaluated at each dose level. Based on the response of subjects in the Stage 1, a target dose is determined for the next stage. Standardized tools will be administered to study both tolerability and efficacy. Efficacy assessments are simply explorative, and are done to look for an effect that warrants specific or different evaluation in the next stage.
- The major purpose of Stage 2 is to assess the safety and tolerability of the Epidiolex at the determined dose, and secondarily to study efficacy, particularly regarding tremor. Stage 2 is a crossover, double-blind, randomized controlled trial (RCT) with 50 subjects.

Our **Hypotheses** are:

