### Assessment of tolerability of each dose level

Tolerability will be assessed at each dose via collection of adverse events during administration of the standardized phone script by appropriate study staff. Severity of adverse events will be graded according to the Common Terminology Criteria for Adverse Events (CTCAE), which is published by the National Cancer Institute (NCI) of the National Institutes of Health (NIH):

Grade 1: Mild; asymptomatic or mild symptoms; clinical or diagnostic observations only; intervention not indicated.

Grade 2: Moderate; minimal, local or noninvasive intervention indicated; limiting age-appropriate instrumental ADLs. Instrumental ADLs refer to preparing meals, shopping for groceries or clothes, using the telephone, managing money, etc.

Grade 3: Severe or medically significant but not immediately life-threatening; hospitalization or prolongation of hospitalization indicated; disabling; limiting self care ADLs. Self care ADLs refer to bathing, dressing and undressing, feeding self, using the toilet, taking medications, and not bedridden.

Grade 4: Life-threatening consequences; urgent intervention indicated.

Grade 5: Death related to AE.

The protocol for dose adjustments, maintenance and discontinuation based on adverse effects is as follows:

- For subjects with a grade 1 adverse event the dose will be increased by up to 5 mg/kg/day, or if they are on the maximal targeted dose (20 mg/kg/day) it will be continued.
- For subjects with a grade 2 adverse event the dose will be reduced by 5 mg/kg/day or less.
- For subjects with a grade 3 or 4 adverse event that the Investigator determines is unrelated, the dose will be continued. When the adverse event is stabilized or resolved, e.g., subject is stable after a hip fracture repair, the dose will be increased unless they are already on the maximum targeted dose.
- For subjects with a grade 3 or 4 adverse event that the Investigator determines is related the study drug will be stopped and not restarted.

The Investigator will determine relatedness as described in Section IV. C.8, and will consider the adverse event related if she determines there is at least a reasonable possibility.

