25 mg/kg/day). During phone calls subjects are monitored for adverse events, as well as changes in medical history and concomitant medications. Subjects are also called 3 days after stopping the study drug to check for signs of withdrawal. Further, in case CBD alters the reliability of self - report, repeated measures will be taken of a set of tests three times: at baseline, low dose and high dose. During the 10 days that subjects are on a low dose the measurements will be taken on the 3rd and 9th day by phone and at the visit on the 10th to 15th day. During the 28 days on high dose the measurements will be taken on the 12th and 22nd day by phone and at the visit on the 28th +/- 4 days. The phone assessments include the primary outcome (assessment of tolerability) and symptoms of hepatotoxicity, SCOPA-sleep, Anxiety short form, Depression short form, Emotional and behavioral dyscontrol short form, and EQ-5D-5L. At low dose visit (end of 10 days on 5 mg/kg/day), each 20 mg/kg/day visit and each end of treatment phase assessment visits, urinary CBD and metabolites will be tested. To increase compliance with taking study drug, subjects will be asked to fill out a diary at home. The diary will be a record of the date and time subjects take study drug, adverse and beneficial events, and whether they talked to study staff on phone that day, and if so what they were told to do with the dose. Study drug is dispensed at the baseline visit and at the start of the second 7-week treatment phase visit so that subject has enough to take until they return for the low dose visit. At that visit they are given enough to last through 20 mg/kg/day. At the 20 mg/kg/day visit they are given enough for the time on 25/mg/kg/day. As in Stage 1, the purpose of the visit at 20 mg/kg/day is to limit the amount of study drug that is dispensed at any one time and facilitate compliance, safety and drug control. In the instance that a subject does not reach the 20 mg/kg/day dose, due to intolerance, then they will come in when and if they need more study drug to complete 10-15 days on their maximal tolerated dose. If they have enough to last through the 10-15 days then they return for the Final Assessment visit, and therefore have fewer total visits.

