#### Dose escalation strategy:

In each of the two 7-week periods, study product (CBD or placebo) will be started at 5 mg/kg/day and increased as tolerated to a maximum weight-adjusted target dose that is determined as a result of the Stage 1 study. The dose escalation strategy is the same as in Stage 1 for each treatment phase, except that subjects will take 5 mg/kg/day for 10 -15 days, and have a study visit before increasing further. The reason for a range of 10-15 days instead of exactly 10 days is to allow for some flexibility in getting subjects in for the study visit. Then the dose is escalated at 3-day intervals (with 5 mg/kg/day increased each interval) until the subject reaches the maximum target dose or experiences intolerable adverse effects, in which case the dose will be dropped to the last tolerated dose. Tolerability will be assessed on the third day of each dose and the subject is instructed whether or not to change the dose on the next day. The maximal tolerated dose is the dose at which 5 mg/kg/day higher was not tolerated on two trials. When subject achieves the maximal tolerated dose or the maximum targeted dose, they will maintain that dose for 28 +/-4 days.

Urine collection, storage and transfer for cannabis and metabolites test protocol is as described in Stage 1.

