### **Participant stopping rules (Both Stages):**

- If subject cannot tolerate the study drug at any dose level
- if subject develops a CTCAE criteria grade 3 or 4 adverse event per that the Investigator determines is related the study drug
- Pregnancy or breast-feeding
- Requested by subject to terminate treatment
- Failure by the subject to attend consecutive study visits;
- Subject is at significant risk of failing to comply with the provisions of the protocol as to cause harm to self or seriously interfere with the validity of the study results;
- At the discretion of the IRB, Food and Drug Administration (FDA).

If a subject is withdrawn from the study, all efforts will be made to complete the early termination visit that includes efficacy assessments and safety follow-up. In addition, women of childbearing potential will have a post-study pregnancy test performed at the early termination visit.

Withdrawals and the reason for withdrawal will be tabulated by treatment group. The number and percentage of subjects who complete the study will be summarized by treatment group. The number and percentage of subjects who withdraw from the study will be tabulated by original treatment group and last treatment taken at time of withdrawal. Study medication discontinuations will be summarized in a similar fashion.

Subjects will be advised that they are free to withdraw from the study at any time. Reasons that subjects may be withdrawn from the study include the following:

Subject discontinued study medication and wishes to withdraw.

Subject consent is withdrawn.

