3. Standardized assessment tools (MoCA, Cognition assessment battery, Anxiety short form, NPI, SCOPA-Sleep, RBDSQ, QUIP-RS, C-SSRS, Depression short form, Emotional Behavioral dyscontrol short form, Fatigue severity scale, MDS UPDRS, UDysRS, Pain Intensity 3a short form and Pain Intensity 4a short form, IRLS, PDQ-39 and EQ-5D-5L) and lab tests, the data will be analyzed as a simple two-period crossover trial. Means and confidence intervals will be presented for each group \* treatment, and for the change scores in each group. A two sample T-test will compare the means of the two groups, those in the CBD-placebo group vs. those in the placebo-CBD group, on the change scores between period 1 to period 2. The difference between the means of the two group will be equal to twice the treatment effect. More complex situations, including testing for treatment \* order interaction, can be analyzed with longitudinal regression models.
4. Proportion of subjects drop out of the study due to study drug intolerance. Analysis (proportions of subjects drop out of the study due to study drug intolerance in the two groups, treatment vs. placebo) will be mostly descriptive, and proportions and confidence intervals will be calculated. Proportion differences between groups can be compared with the standard test.

The difference between the mean change scores of the two group will be equal to twice the treatment effect. We will test the null hypothesis of no treatment effect. To test and control for a possible time/order effect, longitudinal regression models will be fit with a time/order variable included.

Secondary Specific Aim is to examine the effect of CBD on severity & duration of intractable tremor in PD.

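### Stage 2 counts intolerance as such only when a subject drops out, so it cannot say what proportion tolerated the target dose

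*Combined protocol and SAP*

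**What the plan says.** **Purpose.** Section I, and again section C.1, say the major purpose of Stage 2 is to "assess the safety and tolerability of the Epidiolex at the determined dose".

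**Measures.** Section IV.A (Stage 2, Primary Outcome Measures) lists four:

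1. related adverse events by dose level, compared between CBD and placebo;
2. vital signs, examination, EKG and laboratory tests;
3. the assessment scales;
4. a comparison of "the proportion of subjects that drop out of the study due to study drug intolerance in the two groups".

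Section F (Stage 2) analyses item 4 as "Proportion of subjects drop out of the study due to study drug intolerance", with proportions, confidence intervals and a standard test.

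**Dosing.** Section C.3 (Dose escalation strategy) raises the dose until the subject reaches the target or "experiences intolerable adverse effects, in which case the dose will be dropped to the last tolerated dose". It then fixes an individual ceiling: "The maximal tolerated dose is the dose at which 5 mg/kg/day higher was not tolerated on two trials". The subject stays on that ceiling for 28 ± 4 days. The opening of C.3 also plans for the subject who stays in below a titration step ("In the instance that a subject does not reach the 20 mg/kg/day dose, due to intolerance"), there with 10–15 days on the maximal tolerated dose. Section C.2 (Assessment of tolerability of each dose level) states: "For subjects with a grade 2 adverse event the dose will be reduced by 5 mg/kg/day or less". C.3 carries the Stage 1 escalation strategy into Stage 2 with listed exceptions.

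**Leaving.** Under C.7, the tolerability reasons for stopping a participant are "If subject cannot tolerate the study drug at any dose level" and a related grade 3 or 4 event. Subjects may also ask to stop. C.7 tabulates withdrawals, completion and discontinuation of study medication.

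**The concern.** The purpose is tied to a particular dose, but the one measure that counts intolerance is tied to leaving the study. Between the two is a titration rule designed to keep a subject who cannot tolerate the target in the trial at a lower dose. Such a subject completes the phase and is not an item 4 event.

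The primary aim could therefore be reported with little or no dropout on CBD while an unknown number of subjects never held the target dose. A reader planning a later trial needs the proportion who can be brought to the dose and kept there, and the plan as written does not produce it.

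**Working it through.** **1. The plan's own figure.** The only Stage 2 sample size is for tremor (Sample Size Justification): mean effect 1.625, SD of differences 3, alpha 0.05 (taken as two-sided), 90% power, n = 38. For a paired t-test the noncentrality is (1.625/3) × √38 = 3.34 on 37 df, giving power 0.902 (0.894 at n = 37). Allowing for 10% dropout, 38/0.9 = 42.2, so 43. Both figures reproduce, but they say nothing about tolerability, for which no rate or precision target is given.

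**2. Where a subject who cannot tolerate the target appears in the planned output.**

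| Planned summary | Is the stepped-down subject identified as intolerant? |
|---|---|
| Item 1, related adverse events by dose level | No. The event is recorded, but not marked as dose-limiting. Once stepped down, the subject is not exposed at higher levels. |
| Items 2 and 3 | No. These are group comparisons of measurements. |
| Item 4 | Only if the subject leaves the study. |
| C.7 tables | Only on withdrawal or drug discontinuation. C.2 treats adjustment, maintenance and discontinuation of dose as different things, so a reduction is not a discontinuation. |
| Section F, analyses at highest tolerated dose | No. That dose labels an assessment time and is not itself an outcome. |

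Stage 1 does use each subject's maximal tolerated dose, averaging it to set the Stage 2 target (C.1). Stage 2 determines the same quantity in each phase and has no matching summary.

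**3. Possible size, on assumed rates.** Let T be the proportion on CBD who fail to reach or hold the target because of intolerance, and s the share of those who leave the study. The documents give neither. With n = 50 (C.1), item 4 counts n × T × s and misses the fraction 1 − s.

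| T | Intolerant of target | Counted, s = 10% | Counted, s = 25% | Counted, s = 50% |
|---|---|---|---|---|
| 10% | 5 | 0.5 | 1.25 | 2.5 |
| 20% | 10 | 1 | 2.5 | 5 |
| 40% | 20 | 2 | 5 | 10 |

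The fraction missed is 90%, 75% and 50% for s = 10%, 25% and 50%. It is zero if every intolerant subject leaves.

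**4. One cell in full.** Take T = 20% and s = 10%, with exact (Clopper-Pearson) intervals. Item 4 reports 1/50 = 2% (95% CI 0.1% to 10.6%). A count of subjects not reaching or holding the target reports 10/50 = 20% (95% CI 10.0% to 33.7%).

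**5. What a comparison could detect.** Exact McNemar test, 50 pairs, two-sided 0.05, outcomes assumed independent between phases. For failure rates of 20% on CBD and 5% on placebo, the discordant probabilities are 0.20 × 0.95 = 0.19 and 0.05 × 0.80 = 0.04, and power is 0.52. For 30% and 5% it is 0.90. For rates as low as 5% and 1%, as a dropout measure might give, it is 0.02.

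**The case against.** The strongest reply is that dropout is only one of four measures. Item 1 compares related adverse events between groups by dose level, and tolerability is checked on the third day of each dose, so the events that trigger a step-down are primary data. That is correct, and the point must not be read as saying that intolerance goes unrecorded. But item 1 counts events and does not identify dose-limiting ones. Section F also gives no denominator by dose level, and at the target dose only subjects who tolerated the climb remain. It cannot be turned into a proportion tolerating the target.

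Three stronger readings are tempting, and the documents do not support them.

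- A reader might infer that a stepped-down subject is classed as tolerant, or that Stage 2 would declare the dose tolerated on low dropout alone. No rule does either, and the primary outcome is mostly descriptive.
- A reader might infer that most intolerance is missed. Related grade 3 or 4 events do stop the drug, and subjects may ask to leave. The split between leaving and stepping down is not given, so *most* would require s below 50%, which is an assumption.
- A reader might scale up the C.1 example, a Stage 1 mean of 17.4 against a target of 20. In 10 subjects the shortfall is (20 − 17.4) × 10 = 26 mg/kg/day. At 15 short each, 26/15 = 1.7, so at least 2 subjects fall below target. At one 5 mg/kg/day step each, 26/5 = 5.2, so about 5. With the 2.5 mg/kg/day changes that C.2 allows, ten subjects each 2.5 short average 17.5. A mean near 17.4 thus fits 2 to 10 of 10 below target. The example only illustrates rounding and forecasts nothing for Stage 2.

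It can also be said that the formal aim is tolerability in PD, and that dropout is a fair measure of an as-tolerated regimen. That stands as a reason to keep item 4. It does not answer the purpose stated in sections I and C.1.

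**Conclusion.** The point holds as a gap in the primary measures. Stage 2 as planned cannot state what proportion of subjects tolerated the determined dose, and a low dropout rate could coexist with frequent failure to hold it. This follows from the text alone: item 4 is limited to dropouts, C.3 steps subjects down and keeps them in, and neither C.7 nor section F plans a summary of reductions, target attainment or maximal tolerated dose by treatment. The C.3 rule is enough by itself. That the C.2 grade 2 rule also applies in Stage 2 is a reading of C.3's cross-reference.

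The size is not known. The contrast of 2% with 20% rests on assumed T = 20% and s = 10%, and the share missed is 1 − s whatever T is.

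**What to change.** Keep dropout for intolerance in item 4 of section IV.A and of section F, and add for each treatment phase, by treatment, with confidence intervals:

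- (a) the proportion who reach the target dose and complete maintenance on it without reduction or stopping for an adverse effect, with withdrawal for intolerance counted as failure;
- (b) the proportion with any reduction for an adverse effect;
- (c) the distribution of the maximal tolerated dose.

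Compare CBD with placebo by methods section F already names: McNemar's test for subjects with both phases, or GEE/GLMM using all phases entered, so that subjects who never start the second phase still contribute. Given the power shown above, the estimates and intervals should carry the result.

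Measure (a) needs one agreed target. The opening of C.3 gives 20 mg/kg/day, while later text in C.3 and the Stage 2 schedule of events go to 25. The sponsor must reconcile these first. The two maintenance lengths in C.3 for subjects below target (10–15 days and 28 ± 4 days) also need reconciling.

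The cost is protocol and analysis wording, settled before unblinding. The data are already collected: maximal tolerated dose, diary dose instructions, phone script and returned-drug counts. No dosing rule changes. The small downside is that the reported tolerability rate will look less favourable than a dropout rate.
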